Transforaminal/Posterior Lumbar Interbody Fusion
with the
FlareHawk® Expandable Interbody Fusion Device:
A Retrospective Chart Review Study

NCT04057235

November 15, 2019

	Clinical Protocol	Doc: CP-00001	Rev C
	Transforaminal/Posterior Lumbar Interbody Fusion with the FlareHawk® Expandable Interbody Fusion Device: A Retrospective Chart Review Study	Page 1 of 6	

1. PURPOSE:

1.1. This retrospective study will evaluate the clinical outcomes of patients who have undergone a TLIF or PLIF procedure with a FlareHawk expandable interbody fusion cage(s) to assess the device’s performance and safety when used in accordance with its intended use.

2. SCOPE:

2.1. This study will include patients who underwent 1 or 2 contiguous level TLIF or PLIF procedure with the FlareHawk expandable interbody fusion cage. A total of at least 100 patients from at least three sites will be enrolled based on inclusion/exclusion criteria.

3. REFERENCES:

- 3.1. EN ISO 14155, Clinical investigation of medical devices for human subjects - Good clinical practice
- 3.2. CER-00001, FlareHawk Interbody Fusion System Clinical Evaluation Report
- 3.3. MEDDEV 2.7/1 rev.4, Clinical evaluation: Guide for manufacturers and notified bodies
- 3.4. Bridwell KH, Lenke LG, McEnery KW, Baldus C, Blanke K: Anterior fresh frozen structural allografts in the thoracic and lumbar spine. Do they work if combined with posterior fusion and instrumentation in adult patients with kyphosis or anterior column defects? Spine (Phila Pa 1976) 20:1410–1418, 1995
- 3.5. Noshchenko A, Hoffecker L, Lindley EM, Burger EL, Cain CM, Patel VV. Long-term Treatment Effects of Lumbar Arthrodeses in Degenerative Disk Disease: A Systematic Review With Meta-Analysis. J Spinal Disord Tech. 2015;28(9):E493-521
- 3.6. Ostelo RW, Deyo RA, Stratford P, et al. Interpreting change scores for pain and functional status in low back pain: towards international consensus regarding minimal important change. Spine. 2008;33(1):90-4
- 3.7. Yavin D, Casha S, Wiebe S, et al. Lumbar Fusion for Degenerative Disease: A Systematic Review and Meta-Analysis. Neurosurgery. 2017; 80(5):701-715

	Clinical Protocol	Doc: CP-00001	Rev C
	Transforaminal/Posterior Lumbar Interbody Fusion with the FlareHawk® Expandable Interbody Fusion Device: A Retrospective Chart Review Study	Page 2 of 6	

4. METHODS/PROCEDURE:

4.1. Study Hypothesis

The primary hypothesis is that study subjects who received the FlareHawk expandable cage(s) through a TLIF or PLIF procedure experienced fusion by 12 months (+/- 3 mo) follow-up, with improvements in clinical outcomes related to pain and/or disability compared to pre-operative scores. Further, the subjects are hypothesized to have not experienced any unforeseen device- or procedure-related adverse events

4.2. Primary Outcome

Proportion of subjects with radiographic arthrodesis at 12 months +/- 3 months as determined using plain radiographic images with assessment based on the Bridwell-Lenke grading system [Bridwell and Lenke et al, 1995].

4.3. Secondary Outcomes

- Change in VAS Leg from preoperative baseline to 12 months +/- 3 months
- Change in VAS Back from preoperative baseline to 12 months +/- 3 months
- Change in Oswestry Disability Index (ODI) from baseline to 12 months +/- 3 months
- Intra-operative and post-operative adverse events

4.4. Study Population

A total of at least 100 patients from at least three sites will be enrolled based on inclusion/exclusion criteria. Homogeneity of data collection and treatment procedures will be ensured prior to combining data from multiple sites. The retrospective chart review will include the full consecutive series of patients who received TLIF or PLIF surgery using the FlareHawk expandable interbody fusion cage between December 1, 2017, and May 31, 2018. Subjects from that consecutive series will be included in the study based on the pre-defined inclusion and exclusion criteria. If at least 100 patients are not included after screening through the pre-defined inclusion / exclusion criteria, the date range will be extended, and the full consecutive series of patients within the new date range will be considered for inclusion. The date range will be extended, as necessary, until at least 100 patients are included. All subjects will have been diagnosed with degenerative disc disease of the lumbar spine that required lumbar interbody fusion procedure at one or two levels as per the opinion of the treating surgeon. All

	Clinical Protocol	Doc: CP-00001	Rev C
	Transforaminal/Posterior Lumbar Interbody Fusion with the FlareHawk® Expandable Interbody Fusion Device: A Retrospective Chart Review Study	Page 3 of 6	

subjects who meet the inclusion criteria and do not meet any of the exclusion criteria will be included in the study.

4.5. Study Procedure

Refer to **Attachment A** for the detailed study protocol.

5. WORST CASE RATIONALE:

5.1. Not applicable

6. SAMPLE SIZE:

6.1. The primary outcome of this study, radiographic arthrodesis, is commonly observed in approximately 80-100% of study subjects for TLIF/PLIF surgeries [FlareHawk CER-00001 Rev C]. With 100 subjects included, if an 88% fusion rate is observed, the 95% confidence interval for fusion success will be 80.2%-93.0%, placing the performance results within the anticipated range. Further, the inclusion of at least 100 subjects will enable the likely detection of adverse events that have a probability of occurrence of at least 1.6%, assuming a power of 80% [MedDev 2.7.1, rev 4]. This detection rate is adequate for this device and study based on the severity and frequency of anticipated adverse events associated with the FlareHawk device [FlareHawk CER-00001 Rev C]. The target sample size for inclusion will be 118 patients, assuming that up to 15% will not have data at the 12 months follow-up, yielding at least 100 patients with data.

7. ACCEPTANCE CRITERIA:

7.1. Inclusion Criteria

Subjects must meet all of the inclusion criteria to be included in this study.

To be a part of this study, the subject must:

- Have been at least 18 years of age and skeletally mature at the time of surgery
- Have had clinical and radiological evidence of degenerative disc disease of the lumbar spine
- Have been treated with PLIF or TLIF surgery using the FlareHawk expandable interbody cage(s) at 1 or 2 contiguous levels from L2 to S1

	Clinical Protocol	Doc: CP-00001	Rev C
	Transforaminal/Posterior Lumbar Interbody Fusion with the FlareHawk® Expandable Interbody Fusion Device: A Retrospective Chart Review Study	Page 4 of 6	

- Have been treated using the FlareHawk expandable interbody fusion cage, according to the approved labeling, between December 1, 2017, and May 31, 2018

7.2. Exclusion Criteria

Subjects must not meet any of the following exclusion criteria to be included in the study:

- Have a history of fusion surgery at the study level(s) prior to treatment with the FlareHawk device(s)
- Have had spondylolisthesis unable to be reduced to grade 1 as part of the surgical procedure
- Have had surgery with the FlareHawk device(s) at more than 2 levels
- Have had surgery with the FlareHawk device(s) at levels outside the range of L2 to S1
- Have been treated with any bone grafting material other than autogenous or allogenic bone graft in the FlareHawk device(s) and surrounding disc space
- Have any contraindications listed in the approved labeling

8. PERSONNEL/EQUIPMENT:

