[name] is a private practice orthopedic surgeon. He represents the majority of orthopedic spine surgeons in the community with an emphasis on degenerative spine and will does some basic deformity. [name] uses a mini-open approach for his TLIF insertion, and a specialized retractor for visualization. [name] has taught many US courses and is recognized in the Savannah community as one of the top local physicians.

3.8 Subject Eligibility Criteria:

The principal investigator at each site is responsible for verifying that study subjects meet all inclusion/exclusion criteria.

3.9 Inclusion Criteria:

Subjects must meet all of the inclusion criteria to be included in this study.

To be a part of this study, the subject must:

1. Have been at least 18 years of age and skeletally mature at the time of surgery
2. Have had clinical and radiological evidence of degenerative disc disease of the lumbar spine

3. Have been treated with PLIF or TLIF surgery using the FlareHawk expandable interbody cage(s) at 1 or 2 contiguous levels from L2 to S1
4. Have been treated using the FlareHawk expandable interbody fusion cage, according to the approved labeling, between December 1, 2017, and May 31, 2018

3.10 Exclusion criteria:

Subjects must not meet any of the following exclusion criteria to be included in the study:

1. Have a history of fusion surgery at the study level(s) prior to treatment with the FlareHawk device(s)
2. Have had spondylolisthesis unable to be reduced to grade 1 as part of the surgical procedure
3. Have had surgery with the FlareHawk device(s) at more than 2 levels
4. Have had surgery with the FlareHawk device(s) at levels outside the range of L2 to S1
5. Have been treated with any bone grafting material other than autogenous or allogenic bone graft in the FlareHawk device(s) and surrounding disc space
6. Have any contraindications listed in the approved labeling

4. Study Procedure

4.1 Subject Chart Review:

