The study case report form (CRF) is the primary data collection instrument for the study. All data requested on the CRF must be recorded. All missing data must be explained. If a space on the CRF is left blank because the procedure was not done or the question was not asked, write "N/D". If the item is not applicable to the individual case, write "N/A". All entries should be printed legibly in black ink. If any entry error has been made, to correct such an error, draw a single straight line through the incorrect entry and enter the correct data above it. All such changes must be initialed and dated. DO NOT ERASE OR WHITE OUT ERRORS. For clarification of illegible or uncertain entries, print the clarification above the item, then initial and date it. The investigator will be responsible for maintaining adequate, accurate CRFs to guarantee the proper interpretation of the data.

4.3 Data to be Collected:

After confirming inclusion in the study based on the above inclusion and exclusion criteria, data collection from the subject record will include the following, as available:

1. Demographics:

- Age
- Gender at birth
- Diagnosis
- BMI
- Co-morbid conditions
 - Hypertension
 - Diabetes
 - Obesity (BMI \geq 30)
 - Hypercholesterolemia
 - Coronary Heart Disease
 - Hypothyroidism
 - Active or history of cancer
 - Other
- Smoking Status

2. Operative data:
 - Date of Surgery
 - Surgical level(s)
 - Description of all implants and graft materials used, including supplemental fixation if described
 - PLIF or TLIF approach
 - Open, mini-open, or minimally invasive procedure
 - Estimated blood loss
 - Length of surgery
 - Fluoroscopic exposure time
 - Intraoperative device- or procedure-related adverse events
 - Device component breakage/fracture
 - Device malfunction
 - Dural tear/injury
 - Nerve root injury
 - Device-related delay of surgery
 - Retained foreign body
 - Other
 - Length of hospitalization
3. Patient reported outcomes surveys at preoperative baseline and each follow-up:
 - Visual Analog Scale (VAS) back and/or leg – Self Administered Questionnaire
 - Oswestry Disability Index (ODI) - Self Administered Questionnaire
4. Radiographs:
 - Intraoperative post-implantation Lateral and AP X-rays of the lumbar spine
 - 12 months (+/- 3 months) follow-up Lateral, AP, and Flexion-Extension X-rays of the lumbar spine
5. Post-operative device- or procedure-related adverse events
 - Infection
 - Donor site pain
 - Complex Regional Pain Syndrome

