2. Has the subject been diagnosed with degenerative disc disease of the lumbar spine based on clinical and radiological evidence?	 Yes	 No
3. Has the subject been treated with PLIF or TLIF surgery using the FlareHawk expandable cage(s) at 1 or 2 contiguous levels from L2-S1?	 Yes	 No
4. Has the subject undergone surgery using the FlareHawk expandable interbody fusion cage, according to approved labeling, prior to September 30, 2018?	 Yes	 No
All inclusion criteria must be answered "Yes" to proceed to completing the remaining fields. If any inclusion criteria were answered "No" do not collect additional data.		

EXCLUSION CRITERIA		
1. Does the subject have a history of fusion surgery at the study level(s) prior to treatment with the FlareHawk device(s)?	 Yes	 No
2. Did the subject have spondylolisthesis unable to be reduced to grade 1 as part of the surgical procedure?	 Yes	 No
3. Has the subject had surgery with the FlareHawk device(s) at more than 2 levels?	 Yes	 No
4. Has the subject had surgery with the FlareHawk device(s) at levels outside the range of L2- S1?	 Yes	 No
5. Has the subject been treated with any bone grafting material other than autogenous or allogenic bone graft in the FlareHawk device(s) and surrounding disc space?	 Yes	 No
6. Did the subject have any contraindications listed in the approved labeling?	 Yes	 No
All exclusion criteria must be answered "No" to proceed to completing the remaining fields. If any exclusion criteria were answered "Yes" do not collect additional data		

ELIGIBILITY		
Did the Subject meet the Eligibility Criteria?	 Yes	 No

Clinical Site Number: Subject Number:

Case Report Form
Integrity Implants FlareHawk® Study
Baseline Data – Visit 1

Page 1 of 3

VISIT 1 – BASELINEDATE OF VISIT: //
MM DD YYYY**DEMOGRAPHIC DATA**Date of Birth: //
MM DD YYYY Gender at Birth: Female
Male
Height: in. Weight: lb.**SMOKING STATUS**Non-smoker Active smoker History of smoking Not Recorded **COMORBID CONDITIONS**Hypertension Diabetes Obesity (BMI ≥ 30)

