(Open to Close)Estimated Blood Loss: cc./ml.Length of Hospitalization: daysFluoroscopic Exposure Time: min.**TYPE OF PROCEDURE**Operative Procedure: Open Mini-open Minimally Invasive Operative Approach: PLIF TLIF Number of Levels: One Two Surgery Levels: L2-L3 L3-L4 L4-L5 L5-S1 **IMPLANT(S) USED****Implant #1**

Shell Catalog # _____

Shim Catalog # _____

Shell Lot # _____

Shim Lot # _____

Implant #2NA

Shell Catalog # _____

Shim Catalog # _____

Shell Lot # _____

Shim Lot # _____

Implant #3NA

Shell Catalog # _____

Shim Catalog # _____

Shell Lot # _____

Shim Lot # _____

Implant #4NA

Shell Catalog # _____

Shim Catalog # _____

Shell Lot # _____

Shim Lot # _____

GRAFT MATERIALGraft Materials Used: Allograft Autograft Mix of Allograft/Autograft

Clinical Site Number:

Subject Number:

Case Report Form
Integrity Implants FlareHawk® Study
Surgery – Visit 2

SUPPLEMENTAL FIXATION

Supplemental Fixation Used (check one): Unilateral Bilateral

Description of Construct: _____

ADVERSE EVENTS (AEs)

Did any intra-operative adverse events occur? Yes No

If "Yes", add adverse event to **Intra-Operative AE Log**.

DELAY OF SURGERY

Device Related Delay of Surgery: Yes No

If yes, how many minutes? min.

If yes, cause of delay? _____

INSTRUMENTATION

Were there any reported issues with instrument(s)? Yes No

If yes, please provide the catalog and lot number below as well as the description of the issue with the instrument(s):

Catalog # _____ Description of issue: _____

Lot # _____

Not Recorded

Clinical Site Number:

Subject Number:

Case Report Form
Integrity Implants FlareHawk® Study
Surgery – Visit 2

RADIOGRAPHS

Are intra-operative, post-implantation X-rays available on CD? Yes No

X-ray views taken (*check those that apply*): AP Lateral

If X-rays are available, has the CD been provided to the evaluators? Yes No

ADDITIONAL COMMENTS

Please add any other pertinent information regarding the surgical procedure, the device/instruments or any safety concerns:

Clinical Site Number:

Subject Number:

Case Report Form
Integrity Implants FlareHawk® Study
Follow-up – Visit 3

Page 1 of 3

VISIT 3 – 12 MONTHS (+/- 3MONTHS)

DATE OF VISIT: / /
MM DD YYYY

RADIOGRAPHS

Are 12-month X-rays available on CD? Yes No

X-ray views taken (check those that apply): AP Lateral Flexion/Extension

If X-rays are available, has the CD been provided to the evaluators? Yes No

ADVERSE EVENTS (AEs)

Did any post-operative adverse events occur? Yes No

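### The level criteria count only FlareHawk levels, so a patient with another cage or fusion at a further level in the same operation can be included and is not reliably identifiable

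*Combined protocol and SAP*

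**What the plan says.** **Itemised criteria.** Protocol 7.2 excludes patients who "Have had surgery with the FlareHawk device(s) at more than 2 levels" and those who "Have had surgery with the FlareHawk device(s) at levels outside the range of L2 to S1". The level inclusion criterion in 7.1 also refers to surgery using the FlareHawk cage at one or two contiguous levels. Attachment A 3.9 and 3.10 repeat these items, and the CRF eligibility page asks: "Has the subject had surgery with the FlareHawk device(s) at more than 2 levels". The only exclusion for other fusion concerns earlier fusion at the study level or levels.

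**Population text.** Protocol 4.4 and Attachment A 3.5 say that every subject had disease that "required lumbar interbody fusion procedure at one or two levels as per the opinion of the treating surgeon". Protocol 2.1 likewise describes a procedure at one or two contiguous levels. Sections 4.4 and 3.5 then state that everyone who satisfies the criteria is to be included.

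**Data capture.** Attachment A 4.3 lists "Description of all implants and graft materials used, including supplemental fixation if described". The surgery CRF has shell and shim catalog and lot numbers for up to four implants, and a level item reading "Number of Levels: One Two Surgery Levels: L2-L3 L3-L4 L4-L5 L5-S1". It also has free text for the fixation construct and for general comments.

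**Analysis.** Protocol 9.2 and Attachment A 6.2 analyse VAS and ODI change per patient. They summarise the rate of each type of adverse event and compare it with literature on other PLIF and TLIF cages. Neither section has a rule for patients treated at other levels.

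**The concern.** Two parts of the plan define the population differently, and the screening checklist carries the looser definition. A patient with a FlareHawk cage at one level and something else done at another can pass every item.

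Pain, disability and most adverse events belong to the whole operation and cannot be divided by level. If such patients are pooled without being marked, part of what is reported as the outcome of FlareHawk surgery may come from another maker's cage or a further fused level. The adverse event comparison is also blurred, because a study patient may carry one of the very cages used as the literature comparator.

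**Working it through.** This is mainly a comparison of texts. The arithmetic shows what the fix could cost and how large a shift might be, on stated assumptions.

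**1. Test cases against the text.**

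- *FlareHawk at L5-S1, another maker's cage at L4-L5.* There is one FlareHawk level, within L2-S1, and no criterion mentions other cages, so the checklist admits the patient. The population text does too, since interbody fusion was at two levels.
- *FlareHawk at one level, posterolateral fusion at further levels.* The checklist admits the patient. The population text counts interbody fusion, so it does not clearly exclude the patient.
- *FlareHawk at one level, other cages at two or more further levels.* Every item that counts FlareHawk levels is answered acceptably. The population text is contradicted. The plan conflicts with itself here.

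In all three cases the requirement for use according to approved labeling, and the exclusion for labeling contraindications, might remove the patient. That text is not available.

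**2. Can such patients be found afterwards?** The CRF implant fields fit FlareHawk shells and shims. The level item does not say whether it means all operated levels or FlareHawk levels. No item asks about other fused levels or devices. Free text and radiographs may reveal some cases, but not reliably.

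**3. Which outcomes are exposed?** VAS and ODI are whole-patient scores. The post-operative adverse event log has no level field, and its relatedness classes are device, procedure and not related, with none for another implant. The planned summary does not use the classes. The radiographic reviewer form marks as not applicable any level without a FlareHawk device, so fusion at other levels is not counted.

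**4. The plan's sample-size figures (protocol 6.1, Attachment A 3.6) reproduce and are unaffected.**

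- Wilson interval, (p + z²/2n ± z√(p(1−p)/n + z²/4n²)) / (1 + z²/n), with p = 0.88, n = 100, z = 1.96: 80.2% to 93.0%, as stated.
- Chance of at least one event at a 1.6% rate: 1 − 0.984^100 = 0.801, against 80% stated.
- 100 / 0.85 = 117.6, rounded up to 118, as stated.

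**5. Cost if such patients were removed.** The share s is an assumption; the documents give none. Evaluable n = 100(1 − s), and the adverse event rate detectable with 80% probability is 1 − 0.2^(1/n). The number meeting the present criteria that is needed to keep 118 is 118/(1 − s), rounded up.

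| s | n | Wilson CI at 88% | Detectable rate | Needed for 118 |
|---|---|---|---|---|
| 5% | 95 | 79.9–93.1% | 1.7% | 125 |
| 10% | 90 | 79.7–93.2% | 1.8% | 132 |
| 20% | 80 | 79.1–93.4% | 2.0% | 148 |

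**6. Illustrative shift in an adverse event rate.** Assume a rate of 10% in patients treated at FlareHawk levels only and 20% or 30% in the others. The pooled rate is (1 − s) × 0.10 + s × 0.20 or 0.30.

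- s = 5%: 10.5% to 11%
- s = 10%: 11% to 12%
- s = 20%: 12% to 14%

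The Wilson interval for 10 events in 100 patients is 5.5% to 17.4%. All inputs to this step are assumed.

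**The case against.** The best reply is that the plan already limits the operation: scope, population text and the One/Two level item all point to a one- or two-level procedure, and the inclusion criterion can be read that way. This stands to a point. A reader might infer that the plan openly permits long multi-device constructs. It does not: for three or more interbody levels the passages conflict. But the population text leaves a two-level patient with mixed cages, or added non-interbody fusion, unaddressed.

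Other stronger readings also fail:

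- *Adverse events are credited to the device.* Relatedness is recorded for each event, and the not-related class covers events explained by concurrent treatment. What remains is that the summary is not split by that class.
- *The CRF cannot identify these patients.* Free text, films sent to the evaluators, and monitoring against source documents (Attachment A 4.5) could reveal some. What is missing is a dedicated field.
- *The fusion result is biased in the same way.* Only FlareHawk levels are graded, and the documents offer nothing on how a longer construct would alter fusion there.
- *The literature comparator is restricted to one or two levels.* The plan names only other PLIF and TLIF cages.
- *The site list shows that such patients exist.* One investigator has "an emphasis on degenerative spine and will does some basic deformity". That makes other constructs conceivable and shows nothing about actual cases.

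It is also fair to say that the illustrative shift is small beside sampling error at modest shares, and that on those assumptions it would make safety look worse, not better.

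**Conclusion.** The point holds as a gap between the itemised criteria and the population text, with a matching gap between Attachment A 4.3 and the surgery CRF. Patients with another cage or an added fusion at a non-FlareHawk level can pass the checklist unless the unseen labeling removes them, and they cannot be reliably separated later. VAS, ODI and adverse event summaries may therefore be mixed with effects of other devices or levels; the primary fusion outcome is much less exposed.

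The size is undetermined. The documents give neither the share of such patients nor their outcomes, and the direction for VAS and ODI is unknown. This is a worthwhile, inexpensive improvement. It is not a flaw that invalidates the study, and the stated sample-size figures stand.

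**What to change.** 1. Reconcile protocol 7.1 and 7.2, Attachment A 3.9 and 3.10, and the CRF checklist with protocol 2.1 and 4.4 and Attachment A 3.5, so that the one-or-two-level limit counts all levels fused in the index operation.
2. Add one line to the surgery CRF, filled from the operative note, for other levels fused and other interbody devices. Attachment A 4.3 already asks for all implants. State that the level item means all operated levels.
3. In protocol 9.2 and Attachment A 6.2, report VAS, ODI and adverse events with and without patients who had any non-FlareHawk interbody device or fusion at another level. This does not require excluding every mixed-device patient, which would be a debatable change of population.

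The cost is a little more chart abstraction and one further set of summaries. Some patients may be lost under item 1. How many is unknown, but the existing date-range extension can replace them.
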